8.1.5 INTERIM ANALYSIS

Interim analyses will be performed to support regulatory submission(s) and as needed to support conferences, presentations, or publications. No pre-stated study stopping rules are planned.

8.2 PRIMARY DATA ANALYSES

Endpoints will be analyzed using the ITT analysis set. Additional supportive analyses will be conducted in the PP analysis sets for the primary safety and effectiveness endpoints. All available data will be used for each endpoint and no imputations of data are planned.

The primary endpoint of clinical success (defined as cessation of bleeding post-embolization and absence of re-bleeding at the treated site requiring re-intervention [i.e., repeat embolization or additional surgery], within 24 hours) will be presented as frequency and percentage.

Endpoint Derivation:

- “Was there a re-intervention to treat bleeding?” is checked NO, **AND**
- “Was occlusion of the treated area (as seen on post-embolization angiogram) successful?” is checked YES, **AND**
- “Did subject have any re-interventions post-procedure through 24 hours post-procedure?” is checked NO

The primary safety endpoint of absence of serious adverse device effect within 24 hours will be presented as frequency and percentage

Endpoint Derivation:

- “Did any serious and device- and/or procedure-related adverse events occur during the procedure or up to 24 hours post-procedure?” is checked NO

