6.3 Procedural Information

All procedures should be conducted in accordance with site standard of care and patient needs, there are no prohibited concomitant treatments. EmboCube Embolization Gelatin shall be used in accordance with the IFU.

Data collected will include the following:

- Procedure type
- Treated vessel and treated area
- Occlusion of the target area as seen on post-embolization angiography
- Time to hemostasis (TTH) post-EmboCube embolization
- EmboCube Embolization Gelatin size, type and number of units used
- Additional embolic agents used in procedure (e.g., coils, glue, microspheres) - number and type and whether used pre- or post EmboCube
- Transfusion/ use of blood products
- Coagulation status (PT, PTT, INR)
- Repeat embolization or additional surgery to address bleeding within 24 hours
 - Rebleeding due to treated vessel
- Serious and device and/or procedure related adverse events
- Device observations – any observations relating to handling and delivery of EmboCube
- Concomitant anticoagulants and antiplatelet medications

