6.4 Follow-Up

The following data will be collected by review of all medical records available for the period between index procedure and 28 days. In the event the subject is not seen for routine clinic visit or follow-up between 4- and 6-weeks post procedure (28 days +14 days), subjects will be contacted by telephone during this time to confirm their current status and collect safety information.

- Date of discharge post-index procedure
- Concomitant anticoagulants and antiplatelet medications
- Number, type, and timing of additional interventions to treat bleeding
 - Rebleeding due to treated vessel
- Serious and device and/or index procedure related adverse events

Subjects will continue to be treated according to standard routine practice after completion of study.

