5.7 VISIT SCHEDULE

Study participation will last for a total of 28 (0/+14) days (i.e., 28 to 42 days). Follow-up will be by clinic visit or telephone according to site standard of care. Data will be collected from available medical records for baseline, index hospitalization, and standard of care follow-up until 28 days post-procedure. If there is no routine clinic visit or follow-up between 4 and 6 weeks post-procedure (28 [0/+14] days) subjects will be contacted by telephone during this time to collect safety follow-up data to 28 days.

A summary schedule of the data collection for tests and evaluations is provided in Table 1. Data from tests and evaluations performed outside of standard of care will not be collected.

Table 1. Data Collection Schedule

Data	Pre-operative/ baseline	Procedure to 24 hours	28 (0/+14) days follow-up ¹
Informed consent ²	X		
Demographics	X		
Diagnosis (i.e., cause and location of bleeding or hemorrhage)	X	X	
Procedural information		X	
Clinical Success		X	
Technical success		X	
EmboCube use (i.e., size, type, and amount)		X	

Data	Pre-operative/ baseline	Procedure to 24 hours	28 (0/+14) days follow-up ¹
No/type of other adjuvant embolic employed		X	
Device- and/or procedure-related serious adverse events		X	X
Occurrence of re-intervention to control bleeding at the treated site		X	X
Concomitant antiplatelet and anticoagulant medications	X	X	X

¹If a subject does not have a clinic visit at the site between 4 and 6 weeks (i.e., 28 to 42 days), the subject will be telephoned to collect information on potential device-related adverse events and re-interventions.

²Subject will be asked to provide written informed consent for data collection either pre-operatively or prior to hospital discharge.

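### The first re-intervention item in the 24-hour clinical success derivation has no stated window, so read literally it lets later re-interventions count as 24-hour failures

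*SAP*

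**What the plan says.** SAP 8.2 defines the primary performance endpoint as "cessation of bleeding post-embolization and absence of re-bleeding at the treated site requiring re-intervention", limited to 24 hours. Protocol 4.1.1 and SAP 7.1.1 agree.

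The derivation in SAP 8.2 requires all three of the following:

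1. "Was there a re-intervention to treat bleeding" is NO.
2. The question on successful occlusion at the post-embolization angiogram is YES.
3. "Did subject have any re-interventions post-procedure through 24 hours post-procedure" is NO.

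Item 3 carries its own window. Item 1 names no window, visit or form.

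Re-intervention data extend well past 24 hours. In Table 1 of both documents, the row "Occurrence of re-intervention to control bleeding at the treated site" (SAP wording) is marked at the procedure-to-24-hours column and again at the 28-day follow-up. For subjects without a clinic visit in that period, the SAP footnote says "the subject will be telephoned to collect information on potential device-related adverse events and re-interventions". SAP 5.7 adds: "Study participation will last for a total of 28 (0/+14) days".

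Protocol 6.3 lists a procedural item with a limit, "Repeat embolization or additional surgery to address bleeding within 24 hours". Protocol 6.4 lists, for the period from index procedure to 28 days, "Number, type, and timing of additional interventions to treat bleeding". Both sections also record whether the rebleeding came from the treated vessel.

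**The concern.** The endpoint stops at 24 hours, but one of its three components has no stated end. Because the items are joined by AND, a YES on item 1 makes the subject a failure even when item 3 is NO. If item 1 is filled from, or updated by, follow-up data, a 24-hour outcome is mixed with a 28-day one under the 24-hour name.

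The wording of item 1 does not settle the matter. Its reference to treating bleeding is closer to the 28-day item in Protocol 6.4 than to the 24-hour item in Protocol 6.3. Two programmers working from SAP 8.2 alone could therefore take item 1 from different forms and report different primary results from the same data.

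**Working it through.** **Logic check.** Take a subject whose angiogram shows occlusion, who has no re-intervention up to 24 hours, and who is re-embolized at the treated site on day 10. By definition this is a clinical success. Item 2 is YES and item 3 is NO, so item 1 decides:

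| Period covered by item 1 | Answer to item 1 | Derived result | Agrees with definition? |
|---|---|---|---|
| Index procedure only | NO | Success | Yes |
| Post-procedure to 24 hours | NO | Success | Yes |
| Any time in the study (literal reading) | YES | Failure | No |

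On the second reading item 1 is redundant, since item 3 already covers any re-intervention in that period. Item 1 adds information only if it covers the procedure itself, which is consistent with the endpoint, or the time after 24 hours, which is not. The SAP does not say which.

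**Comparison with neighbouring derivations.** The primary safety item in SAP 8.2 states that it covers the procedure and the following 24 hours. The late adverse event item in SAP 8.3 states that it starts from the 24-hour contact. Item 1 has no such phrase.

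**The plan's own figure.** SAP 5.5 gives a reference rate of 92%, an expected rate p = 0.90, a margin of 10% (lower bound 0.92 − 0.10 = 0.82), alpha 0.05 and power 80%. With one-sided alpha and variance at p:

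n = (1.645 + 0.842)² × 0.90 × 0.10 / (0.90 − 0.82)² = 86.9, so 87 evaluable.

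Allowing for 15% loss gives 87 / 0.85 = 102.4, so 103, or 87 × 1.15 = 100.05, so 101. Both are close to the stated 100. The 90% is set for the 24-hour endpoint, so limiting item 1 to 24 hours leaves the sample size unchanged.

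**Size if the literal reading were applied.** Let q be the share of 24-hour successes with a later re-intervention. The documents give no value, so the range is assumed. Reported rate = 0.90 × (1 − q).

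| q (assumed) | Reported rate | Successes reclassified per 100 subjects (90 × q) |
|---|---|---|
| 0% | 90.0% | 0 |
| 1% | 89.1% | 0.9 |
| 2% | 88.2% | 1.8 |
| 3% | 87.3% | 2.7 |
| 5% | 85.5% | 4.5 |
| 10% | 81.0% | 9.0 |

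The effect runs one way: an over-long window can add failures but cannot remove any.

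**The case against.** The strongest reply is that the derivation quotes eCRF field labels, and a field takes its visit from the form it sits on. A label without a window is not necessarily a field without one. Item 2 names no visit either, and nobody would read it as a 28-day item. The eCRF is not among the documents.

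Several features favour a benign reading. The clinical success row of Table 1 is marked only at procedure to 24 hours in both documents. The definition stated just above the derivation says 24 hours. The three items can be read in time order, with item 3 starting after the procedure, so item 1 may cover the procedure itself.

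All of this stands. It shows that a coherent reading exists and may well be the intended one. A reader might infer from the missing window that day-28 events will enter the primary endpoint, or that item 1 can serve no other purpose. The documents support neither inference.

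The reply does not supply the missing window. The SAP is the document that fixes the primary derivation, and nothing in it ties item 1 to the procedure form or to 24 hours.

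**Conclusion.** The point holds as a defect in a written rule: taken literally, the derivation in SAP 8.2 departs from the endpoint it implements. That the departure would occur in practice is not shown, because it depends on an eCRF form that the documents do not include.

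The size is unknown. The fall from 90% to between about 89% and 81% rests on an assumed late re-intervention rate of 1% to 10% among 24-hour successes, on the planned 90% being the true 24-hour rate, and on item 1 picking up every later event. Any such error would understate the device's success.

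A reader might also infer that a result near 81% would fail the study against the 82% bound. The documents do not support that. The bound follows from the sample size parameters, while Protocol 9.2 and SAP 8.2 plan only a frequency and percentage for this endpoint and specify no test against it. The correction is worth making because it concerns the primary endpoint and costs little.

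**What to change.** Derive the re-intervention component of clinical success in SAP 8.2 from recorded timing. Count as a failure any repeat embolization or additional surgery for re-bleeding at the treated site from the index embolization through 24 hours post-procedure, whichever form records it. State that later re-interventions do not enter the primary endpoint.

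Two features of this wording matter. It keeps the treated-site condition, which the definition contains but neither re-intervention item does. It also starts at the index embolization, so a re-intervention during the procedure is not lost.

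If item 1 is a procedure-form field, name that form in the SAP and keep the item for the intraprocedural period.

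The cost is SAP wording and programming. Protocol 6.4 already collects the timing of interventions but does not say whether this includes clock time. Where only dates are recorded, sites would have to supply clock times for re-interventions on days 0 and 1. The sample size does not change.

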4 ENDPOINTS AND SUBJECT POPULATION

4.1 Primary Outcome Measures

4.1.1 Primary effectiveness endpoint

The primary performance endpoint will be clinical success defined as cessation of bleeding post-embolization and absence of rebleeding at the treated site requiring reintervention (repeat embolization or additional surgery), within 24 hours.

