6 DATA COLLECTION PROCEDURES

6.1 Visit Schedule

Study participation will last for a total of 28 days (+14 days). Follow-up will be by clinic visit or telephone according to site standard of care. Data will be collected from available medical records for baseline, index hospitalization, and standard of care follow-up until 28 days post-procedure. If there is no routine clinic visit or follow-up between 4 and 6-weeks post procedure (28 days +14 days) subjects will be contacted by telephone during this time to collect safety follow-up to 28 days.

A summary schedule of the data collection for tests and evaluations is in Table 1. Data will only be collected if tests and evaluations are completed per standard of care.

Table 1 Data Collection Schedule

Data	Pre-operative/ baseline	Procedure to 24 hours	28-day follow-up ² (28 to 42 days)
Informed consent ¹	X		
Demographics	X		
Diagnosis, i.e., cause and location of bleeding or hemorrhage	X	X	
Procedural information		X	
Clinical Success		X	
Technical success		X	
EmboCube use (size, type, and amount)		X	
No/type other adjuvant embolics employed		X	
Device and/or procedure related serious adverse events		X	X
Occurrence of re-intervention to control bleeding at the treated site		X	X
Concomitant antiplatelet and anticoagulant medications	X	X	X

¹ Subject will be asked to provide written informed consent for data collection either preoperatively or prior to hospital discharge.

² If subject is not seen by site between 4-6 weeks (28 to 42 days) for clinical visit, subject will be telephoned to collect information on potential device related adverse events and reinterventions.

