7 OUTCOME VARIABLES

7.1 PRIMARY OUTCOMES

7.1.1 PRIMARY EFFECTIVENESS ENDPOINT

The primary performance endpoint will be clinical success defined as cessation of bleeding post-embolization and absence of re-bleeding at the treated site requiring re-intervention (i.e., repeat embolization or additional surgery) within 24 hours.

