8.3 SECONDARY DATA ANALYSES

All secondary endpoints will be tabulated. Means, SDs, and sample size will be used to summarize continuous variables. Distributions of continuous data will be examined and if non-normality is exhibited, medians and interquartile ranges will be presented. Frequencies and percentages will be used to summarize categorical variables. All available data will be used for each endpoint and no imputations will be performed.

Incidence of adverse events to 24 hours post-operative (serious and device- and/or procedure-related)

Endpoint Derivation:

- Serious adverse events as reported by the site, **AND**
- “Seriousness” is checked as anything other than “Not Serious”, **AND**
- Relationship to study device **AND/OR** relationship to study procedure is “Definitely related”

Incidence of adverse events between 24 hours and 28 days post-operative (serious and device- and/or procedure-related)

Endpoint Derivation:

- “Were there any serious and device- or procedure-related adverse events since the 24-hour contact visit?” is checked YES, **AND**
- Serious adverse events as reported by the site and in which “Seriousness” is checked as anything other than “Not Serious”, **AND**
- Relationship to study device **AND/OR** relationship to study procedure is “Definitely related”

Technical success defined as successful occlusion of the treated site as seen on post-embolization angiography

Endpoint Derivation:

- “Was occlusion of the treated area (as seen on post-embolization angiogram) successful?” is checked YES

Incidence of device observations related to EmboCube

Endpoint Derivation:

- “Was procedure aborted due to device observation?” is checked YES

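### The SAP 8.2 derivation does not compute the clinical success it defines: no derivation item records that bleeding stopped, angiographic occlusion is required instead, and re-intervention is not limited to the treated site

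*SAP*

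**What the plan says.** The definition is consistent across the documents. Protocol 4.1.1 requires "cessation of bleeding post-embolization and absence of rebleeding at the treated site requiring reintervention", within 24 hours. SAP 7.1.1 repeats it, and SAP 8.2 restates it as "defined as cessation of bleeding post-embolization and absence of re-bleeding at the treated site requiring re-intervention".

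Directly below that restatement, SAP 8.2 counts a subject as a success when three items are all satisfied:

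1. "Was there a re-intervention to treat bleeding" is answered NO.
2. "Was occlusion of the treated area (as seen on post-embolization angiogram) successful" is answered YES.
3. "Did subject have any re-interventions post-procedure through 24 hours post-procedure" is answered NO.

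The second item reappears in SAP 8.3 as the only item for a separate secondary endpoint: "Technical success defined as successful occlusion of the treated site as seen on post-embolization angiography".

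The plan also lists data closer to the definition. Protocol 6.3 lists time to hemostasis and, as a sub-item under repeat embolization or surgery for bleeding, whether re-bleeding came from the treated vessel. Table 1 in both documents has separate rows for clinical and technical success, and a row for "Occurrence of re-intervention to control bleeding at the treated site". The SAP 8.2 derivation names none of these.

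**The concern.** The definition has two parts, and the rule departs from both.

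**Cessation of bleeding.** No derivation item asks about it. A NO on re-intervention for bleeding is only indirect evidence that bleeding stopped. Angiographic occlusion, which the definition does not mention, takes its place. Derived clinical success therefore becomes a subset of technical success by construction, although the plan presents them as distinct endpoints.

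**Treated site.** The definition counts only re-bleeding there. The two re-intervention items carry no such limit, and the treated-vessel attribution is not used.

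This is the primary performance endpoint and the one that sizes the study (SAP 5.5). A reader would take the published percentage as the defined clinical success, when it is occlusion without re-intervention.

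**Working it through.** **Definition and rule applied to the same subjects**

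| Subject | Bleeding stopped | Occlusion item | Re-intervention by 24 h | By definition | By the SAP 8.2 rule |
|---|---|---|---|---|---|
| A | yes | YES | none | success | success |
| B | no | YES | none | failure | **success** |
| C | yes | NO | none | success | **failure** |
| D | yes | YES | for bleeding at another site | success | **failure** |
| E | yes | YES | for re-bleeding at the treated site | failure | failure |

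B and C come from replacing cessation with occlusion; D comes from losing the treated-site limit. Two further discrepancies are wording risks only, because the eCRF is not in the documents: item 1 states no 24-hour window, and item 3 is not limited to bleeding.

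**The plan's own figure.** SAP 5.5 gives a reference rate of 92%, an expected rate of 90%, a margin of 10 points (limit 92% − 10% = 82%), alpha 0.05, power 80% and 15% loss. With one-sided alpha and the variance taken at 90%:

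n = 0.90 × 0.10 × (1.645 + 0.842)² / (0.90 − 0.82)² = 0.09 × 6.183 / 0.0064 = 86.94

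Inflation gives 86.94 × 1.15 = 99.98, or 87 / 0.85, which rounds up to 103. The stated 100 is reproduced and is not disputed here.

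**Effect of one misclassified subject.** The documents give no mismatch frequency, so none is assumed. The interval is the two-sided 95% Clopper-Pearson interval named in SAP 8.1: lower limit = Beta(0.025; x, n − x + 1), upper limit = Beta(0.975; x + 1, n − x). The starting point is the planned 90%, at n = 100 and at n = 100 × 0.85 = 85 (85 × 0.90 = 76.5, taken as 77).

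| n | Counted successes | Rate | 95% interval |
|---|---|---|---|
| 100 | 89 (one true success lost) | 89.0% | 81.2 to 94.4 |
| 100 | 90 | 90.0% | 82.4 to 95.1 |
| 100 | 91 (one true failure gained) | 91.0% | 83.6 to 95.8 |
| 85 | 76 (one true success lost) | 89.4% | 80.8 to 95.0 |
| 85 | 77 | 90.6% | 82.3 to 95.8 |
| 85 | 78 (one true failure gained) | 91.8% | 83.8 to 96.6 |

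One subject is 1/100 = 1.0 point or 1/85 = 1.2 points. At either n, one lost success takes the lower limit from just above 82% to below it.

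**Sizing rationale under assumed shifts (illustration only).** Suppose the derived rate q falls below a true 90% by a net 0, 1, 2, 3 or 5 points. Then Φ[(q − 0.82) / √(q(1 − q)/85) − 1.645] gives power of 79%, 66%, 52%, 39% or 19%. The shifts are assumptions, and the SAP plans no test against 82%.

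**The case against.** The strongest reply is that occlusion on angiogram plus no re-intervention is a sensible working proxy. The device is indicated to occlude flow in order to control bleeding, and most of the mismatches (subjects C and D, and re-intervention for another reason) count against the device. The only favourable error named needs continued bleeding, a YES on occlusion and no re-intervention for 24 hours. The eCRF is also unseen: a form heading may limit the re-intervention items to the treated site, as the Table 1 row does, and the clinical success row suggests that a direct field may exist. Finally, the analysis is primarily descriptive (Protocol 9), the mismatch frequency is unknown, and procedure and re-intervention data will be tabulated and listed (SAP 9.1, 9.2).

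Part of this stands. The gap is in the derivation, not in all data collection. The size is unknown, no planned test is affected, and the planned tables and listings give partial visibility.

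The rest does not remove the point. A proxy that the SAP never declares is not the defined endpoint. No form heading can turn a question about occlusion into one about cessation. On site, Protocol 6.3 places the treated-vessel question beneath re-intervention for bleeding, which suggests that the parent question covers bleeding anywhere; the rule drops that attribution. A clinical success row in Table 1 helps with the repair, but SAP 8.2 does not use it.

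**Conclusion.** The concern holds. The definition and the derivation in SAP 8.2 can classify the same subject oppositely, in both directions, on the primary performance endpoint. This is an error as written, not a missing detail, and must be corrected before analysis. Its net direction and total size cannot be derived from the documents; what can be shown is the per-subject effect above. That effect assumes the planned 90% rate and 85 or 100 evaluable subjects. The consequence is a reported rate and interval that do not describe the stated endpoint. The conclusion on cessation does not depend on the eCRF. The treated-site conclusion takes the items as the SAP words them.

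**What to change.** Rewrite the SAP 8.2 derivation so that success requires both:

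- **Bleeding stopped after embolization.** Take this from time to hemostasis (Protocol 6.3), or from a recorded cessation or clinical-success field if the eCRF has one that is not itself built from the present three items.
- **No repeat embolization or additional surgery within 24 hours for re-bleeding at the treated site.** Use the treated-vessel sub-item, and state that treated vessel is taken as treated site.

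Count hemostasis recorded as not achieved as a failure. The documents do not say that the time-to-hemostasis field can hold that value, so check this against the eCRF. State in advance how a blank is handled and report the number of blanks; otherwise the non-missing denominator in SAP 8.1 and the absence of imputation in SAP 8.1.3 would drop those subjects. Keep the occlusion item for technical success only.

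If the eCRF holds no usable cessation item, label the result as angiographic occlusion without re-intervention to 24 hours, restrict the re-intervention items to the treated site and to 24 hours, and do not present it as the defined clinical success.

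The cost is SAP wording and programming, or a relabel. The downside is that data are collected only as standard of care provides (Protocol 6.1), so some subjects may lack hemostasis data and the evaluable number may fall.

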1.2 Literature Summary

Gelatin based embolics are among the earliest materials utilized for therapeutic arterial embolization. Due to absorbability, this material is the preferred device when shorter occlusion time is the objective, a permanent implantable is not desired, or distal super selective targeting is not the goal. A principal use of resorbable embolic material is the management of hemorrhage from spontaneous conditions, instrumentation, or trauma. In each of these uses the goal typically is to achieve an immediate plugging of the source of blood loss without causing permanent ischemia. A large number of publications of case studies and cohort evaluations of comparable gelatin embolics demonstrate clinical success rates of 80-100% (depending on condition) in the control of acute bleeding and massive hemorrhage.

The indication of control of hemorrhaging and bleeding and pre-operative embolization covers a wide range of causes (trauma, postpartum, instrumentation, idiopathic, etc.) in a variety of anatomical locations (limbs, uterus/reproductive tract, viscera, etc.), and in populations ranging from healthy to those with multiple comorbidities or polytrauma. Frequently the bleeding occurs in an emergency situation, requiring rapid medical response and treatment. Although comparable resorbable gelatin embolics have been used to stop bleeding and hemorrhaging and for pre-operative embolization for decades, EmboCube is a more recent product.

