7.2 Reportable Adverse Events

For the purpose of this study, events which meet the definition of both serious adverse events and that are potentially device-related and/or procedure-related will be reported.

All deaths will be reported as SAE regardless of Investigator assessment of causality.

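### The SAP's clinical-success derivation has no survival, bleeding-cessation or re-bleeding item, so an occluded subject who bleeds to death within 24 hours without a second procedure can be scored a success

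*SAP*

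**What the plan says.** SAP 7.1.1 defines the primary performance endpoint as "cessation of bleeding post-embolization and absence of re-bleeding at the treated site requiring re-intervention (i.e., repeat embolization or additional surgery) within 24 hours". The wording in Protocol 4.1.1 is the same in substance.

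SAP 8.2 turns this into three conditions, all of which must hold:

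1. "Was there a re-intervention to treat bleeding" is NO.
2. "Was occlusion of the treated area (as seen on post-embolization angiogram) successful" is YES.
3. "Did subject have any re-interventions post-procedure through 24 hours post-procedure" is NO.

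On missing data, SAP 8.2 says "All available data will be used for each endpoint and no imputations of data are planned", and SAP 8.1 bases percentages on subjects with non-missing values.

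Deaths are handled as safety data. Protocol 7.2 states "All deaths will be reported as SAE regardless of Investigator assessment of causality", and Protocol 7 extends this to 28 days. No section of either document carries a death into the clinical-success derivation.

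Protocol 1.2 describes use in emergencies and massive hemorrhage, "in populations ranging from healthy to those with multiple comorbidities or polytrauma".

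**The concern.** The only post-procedure event that can make a subject a failure is a second procedure. Death prevents that procedure. A subject who re-bleeds and survives to a repeat embolization is a failure, while one who re-bleeds and dies first can be a success. The worst outcome of the treated condition is then scored better than a less severe one, on the primary performance endpoint. The per-protocol analysis uses the same derivation and does not correct it.

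The safety endpoints need not catch the case. If the site attributes the death to the underlying condition, the primary safety item in SAP 8.2 can be answered NO, and the secondary adverse-event rules in SAP 8.3 count only events rated definitely related. The death would still appear in the adverse-event listing, but no table planned in SAP 9.1 sets early deaths beside clinical success.

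**Working it through.** **Definition against derivation**

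| Element of the endpoint (SAP 7.1.1) | Item in the SAP 8.2 derivation |
|---|---|
| Bleeding stops after embolization | None; angiographic occlusion stands in for it |
| No re-bleeding at the treated site that requires re-intervention | Only whether a re-intervention took place |
| Status at 24 hours (alive or dead) | None, and none in the definition |

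Protocol 6.3 also plans to collect time to hemostasis and re-bleeding from the treated vessel. The derivation uses neither, and the re-bleeding item is listed beneath repeat embolization or surgery, so it may not capture a re-bleed without a procedure.

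**Applying the rule to a death from bleeding within 24 hours with no second procedure**

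| Occlusion item | 24-hour re-intervention item | Result |
|---|---|---|
| YES | NO | Success |
| YES | Blank | Not derivable; leaves the denominator (SAP 8.1) |
| NO | NO | Not a success |

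The first two rows are the problem. The third is handled correctly.

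**The plan's own figure.** SAP 5.5 gives a reference rate of 92%, an expected rate of 90%, a margin of 10%, alpha 0.05, power 80% and 15% loss. With one-sided alpha and the variance taken at 90%:

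n = 0.90 × 0.10 × (1.645 + 0.842)² / (0.90 − 0.82)² = 0.09 × 6.18 / 0.0064 = 86.9

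86.9 × 1.15 = 100.0, which is the stated 100; the usual inflation, 87/0.85, gives 103. The 82% in the formula is 92% − 10%. It is implied by these inputs and appears nowhere as a success criterion.

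**Size per death.** 1/100 = 1.0 point at n=100; 1/85 = 1.2 points if 15% are lost.

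**Illustration.** Assume the SAP rule scores 90 of 100 subjects as successes and that k of those 90 were deaths from treated-site bleeding within 24 hours. The documents do not give k. The two-sided interval is the Clopper-Pearson interval named in SAP 8.1.

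| k | Rate with the k deaths as failures | Exact 95% CI | One-sided 5% exact lower bound |
|---|---|---|---|
| 0 | 90/100 = 90.0% | 82.4 to 95.1% | 83.6% |
| 1 | 89/100 = 89.0% | 81.2 to 94.4% | 82.5% |
| 2 | 88/100 = 88.0% | 80.0 to 93.6% | 81.3% |
| 3 | 87/100 = 87.0% | 78.8 to 92.9% | 80.1% |

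**Blank-item route.** With k=2 dropped from the denominator the rate is 88/98 = 89.8%, against 88/100 = 88.0% when the deaths are kept as failures. Both routes err upward.

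**The case against.** Several points on the other side stand.

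- **Not every fatal bleed is a success.** A reader might infer that any subject who bleeds to death within 24 hours without a second procedure is scored a success. SAP 8.2 does not support that: failed occlusion already makes the subject a non-success, and a blank 24-hour item removes the subject. The documents do not say how sites complete that item after a death.
- **The prose definition is better than the rule.** Continued bleeding fails the cessation requirement, and a fatal re-bleed can be read as one that required re-intervention even if none was done. This clears the definition in part. It does not clear the derivation, which is what will be programmed.
- **Few such deaths may enter.** Under Protocol 5.2 no data are collected before written consent, and prior consent is expected to be impossible in many cases. Those most likely to die early are the least likely to have consented. The exclusion for poor prognosis concerns co-morbidity rather than the index bleed, so it helps little, but the consent rule probably keeps the count low.
- **No decision turns on 82%.** A reader might infer that one such death makes the study miss its non-inferiority limit. That depends on starting at exactly 90/100 and on the two-sided interval. From 91/100, one reclassified death leaves 90/100, with a lower limit of 82.4%. On a one-sided 5% bound, two deaths are needed. Protocol 9 calls the analysis primarily descriptive, and SAP 8.2 sets no test.
- **Deaths are not hidden.** They are reported to 28 days whatever their cause, and the listings in SAP 9.2 would show them.

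What remains is that a written rule for the primary performance endpoint gives the wrong answer in a foreseeable case, and nothing elsewhere in the plan overrides it.

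**Conclusion.** The point holds for a defined group: subjects with occlusion marked successful who die of bleeding within 24 hours without a second procedure. With both re-intervention items answered NO they count as successes; with the 24-hour item blank they leave the denominator. Both results conflict with the endpoint's cessation requirement, and both can only raise the rate.

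The size is 1 percentage point per death scored as a success at n=100. The number of such deaths is unknown and may be zero; the range of 1 to 3 above is an assumption. The confidence limits show scale only and should not be read as a pass or fail result. The case for changing the rule rests on its direction and on its place in the primary endpoint, not on a predicted count.

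**What to change.** In SAP 8.2, add a fourth condition to the clinical-success derivation: *AND no death within 24 hours post-procedure, unless the death report shows that it was not due to bleeding at the treated site.* State alongside it:

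- A death within 24 hours that is due to treated-site bleeding, or cannot be clearly separated from it, is a failure.
- Such a subject stays in the denominator even if the 24-hour re-intervention item is blank.
- The number of deaths within 24 hours is reported beside the rate, in both the ITT and PP tables.
- A sensitivity rate counts every death within 24 hours as a failure.

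The cost is small: a few lines of SAP text and programming. The reported rate may be slightly lower. Neither document lists a dedicated cause-of-death field, so cause must be read from the death or serious-event report; the default to failure covers unclear cases. The sponsor should also confirm that the independent adjudicator reviews these deaths, because Protocol 10.17 covers all serious and potentially device-related events while Protocol 10.18 speaks of a sample only.

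This condition deals with deaths alone. A surviving subject who re-bleeds and is managed without a procedure would still pass the three check-boxes, so the sponsor should also state whether that outcome meets the definition.
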